4.4.2.1.2 Maximum Overall Intensity

Maximum intensity is derived from the daily intensities computed as described in [Section 4.4.2.1.1](#) and is calculated as the maximum of the daily intensities over the period considered.

Note: The maximum intensity could be considered as “None” (i.e., not a reaction) in the analysis despite being considered a reaction by the Investigator (e.g., Injection site erythema measurement > 0 mm and < 25 mm, in adolescents).

4.4.2.1.3 Presence

Presence is derived from the maximum intensity on the period considered:

- None: No presence
- Grade 1, Grade 2, or Grade 3: Presence
- Missing: Missing presence

Subjects with at least one non-missing presence for a specific endpoint will be included in the analysis. Conversely, those without a non-missing presence will not be included in the analysis of the endpoint.

4.4.2.1.4 Time of Onset

Time of onset is derived from the daily intensities computed as described in [Section 4.4.2.1.1](#). It corresponds to the first day with intensity of Grade 1, Grade 2, or Grade 3.

Note: If a reaction is not continuous (i.e., reaction occurs over two separate periods of time intervened by at least one daily intensity Missing or None) then the time of onset is the first day of the first occurrence.

Time of onset will be displayed by period as follows:

- Injection site reactions (D0-D7): D0-D3, D4-D7
- Systemic reactions (D0-D14): D0-D3, D4-D7, D8-D14

4.4.2.1.5 Number of Days of Occurrence

Number of days of occurrence over the period considered is derived from the daily intensities computed as described in [Section 4.4.2.1.1](#). It corresponds to the number of days with daily intensities of Grade 1, Grade 2, or Grade 3. Number of days of occurrence on the solicited period with a specified intensity may also be derived.

Number of days of occurrence during the solicited period will be displayed by category (range) as follows:

- Injection site reactions (D0-D7): 1-3 days, 4-7 days, 8 days
- Systemic reactions (D0-D14): 1-3 days, 4-7 days, 8-14 days, 15 days

4.4.2.1.6 Overall Number of Days of Occurrence

If a reaction is ongoing at the end of the solicited period, then the overall number of days of occurrence is derived from the daily intensities and the stop date of the reaction after the end of the solicited period. The overall number of days of occurrence is:

- (stop date – last vaccination date) + (number of days of occurrence within the solicited period) – length of the solicited period + 1

If the stop date is missing or incomplete (contains missing data [MD]), the overall number of days of occurrence will be considered as Missing.

Overall number of days of occurrence will be displayed by category (range) as follows:

- Injection site reactions (D0-D7): 2-3 days, 4-7 days, ≥ 8 days, missing
- Systemic reactions (D0-D14): 2-3 days, 4-7 days, 8-14 days, ≥ 15 days, missing

4.4.2.1.7 Ongoing

Ongoing is derived from the last daily intensity of the solicited period computed as described in [Section 4.4.2.1.1](#) and the maximum intensity on the ongoing period. The investigator's ongoing flag is not used because the measurement would determine the ongoing status of the reaction. If the last daily intensity of the solicited period is at least Grade 1 and maximum intensity on the ongoing period is also at least Grade 1, then the reaction is considered ongoing. In any other cases the reaction will not be considered as ongoing.

Note: a reaction could be derived as not ongoing for the analysis despite being considered as ongoing by the Investigator (e.g. when the maximum Injection site erythema measurement after D7 for adolescents is > 0 mm but < 25 mm).

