4.4.2.1 Solicited Reactions

4.4.2.1.1 Daily Intensity

All daily records for solicited reactions will be derived into daily intensity according to the following classification: None, Grade 1, Grade 2, Grade 3, or Missing.

For the derivation of daily intensities the following sequential steps will be applied:

- 1) Solicited reactions (except Fever/Pyrexia) with an investigator presence recorded as "No" and with all daily records missing then all daily intensities will be derived as None.
- 2) For non-measurable solicited reactions, daily intensities will correspond to daily records reported in the clinical database. For measurable solicited reactions the daily measurements reported in the clinical database will be converted based upon the intensity scales defined in

Section 9.2.2.3.2 of the protocol; this assumes a reaction that is too large to measure (non measurable, [NM]) is Grade 3.

Note: The maximum intensity on the ongoing period is derived from the record of the maximum intensity/measurement after the end of the solicited period following the rule described above.

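### SAP 4.4.2.1.7 codes a solicited reaction as not ongoing when its last in-window or its post-window intensity is missing, so missing data can only lower the count of ongoing reactions

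*SAP*

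**What the plan says.** SAP 4.4.2.1.7 makes ongoing status depend on two values. A reaction counts as ongoing only if the final in-window daily intensity and the post-window maximum both reach Grade 1. For everything else, "In any other cases the reaction will not be considered as ongoing". The flag has no third level.

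The investigator's own assessment is set aside: "The investigator's ongoing flag is not used because the measurement would determine the ongoing status of the reaction". A note accepts that "a reaction could be derived as not ongoing for the analysis despite being considered as ongoing by the Investigator". Its example is an erythema below 25 mm after D7; missing data are not mentioned.

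SAP 4.4.2.1.1 derives daily intensity with the "following classification: None, Grade 1, Grade 2, Grade 3, or Missing", and its note applies the same rule to the single post-window record. SAP 5.3.2.4 sends missing solicited intensities back to 4.4.2.1.1, and 5.3.2 says that nothing is replaced unless stated.

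The status feeds SAP 4.4.2.1.6: "If a reaction is ongoing at the end of the solicited period, then the overall number of days of occurrence is derived", using the post-window stop date together with the in-window daily records. The missing category there is triggered only by a missing or incomplete stop date.

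**The concern.** Missing is a defined level and is not Grade 1 or higher, so it falls into the residual clause. One blank cell on D7 or D14, or a blank post-window grade, settles the reaction as not ongoing. That happens even if the other value is graded and the flag or a post-window stop date shows that the reaction continued. In effect the rule imputes the favourable value.

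The SAP treats missing data differently elsewhere. A missing maximum intensity gives a missing presence (4.4.2.1.3), a missing stop date gives missing overall days (4.4.2.1.6), and missing causality is counted as related (5.3.2.2).

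The reason given for dropping the flag is that a measurement decides. That suits erythema, swelling and fever, where a size or temperature below threshold can overrule an impression. Pain, headache, malaise, myalgia and asthenia, five of the eight solicited reactions, are graded and have no measurement (protocol Tables 9.1 and 9.2). At stake are the number of reactions reported as outlasting the solicited window and their overall days.

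**Working it through.** The documents state no figure on this point, so there is none to reproduce. The check enumerates the rule, illustrates scale, and follows one reaction through the SAP's formula.

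**Enumeration.** Inputs: five levels for each field (None, Grade 1, Grade 2, Grade 3, Missing; SAP 4.4.2.1.1) and the two-part condition of 4.4.2.1.7. There are 5 × 5 = 25 combinations.

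| Last daily intensity and post-window maximum | Combinations | Coded by the SAP | Compatible with a truly ongoing reaction |
|---|---|---|---|
| Both Grade 1–3 | 9 | Ongoing | Yes |
| Both recorded, at least one None | 7 | Not ongoing | No |
| Grade 1–3, then Missing | 3 | Not ongoing | Yes |
| Missing, then Grade 1–3 | 3 | Not ongoing | Yes |
| Both Missing | 1 | Not ongoing | Yes |
| One None, the other Missing | 2 | Not ongoing | No |

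Nine combinations contain Missing (3 + 3 + 1 + 2). All nine are coded not ongoing, and seven of them (3 + 3 + 1) could be ongoing. In the other two, the recorded None decides the matter whatever the missing value was. Missing data can therefore lower the ongoing count or leave it alone, but never raise it.

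**Illustration of scale.** Suppose that, among truly ongoing reactions, each field is missing independently with probability m. The rate and the independence are both assumptions. The share coded not ongoing is 1 − (1 − m)²:

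- m = 2%: 1 − 0.98² = 4.0%
- m = 5%: 1 − 0.95² = 9.8%
- m = 10%: 1 − 0.90² = 19.0%

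**One reaction.** The 4.4.2.1.6 formula is (stop date − vaccination date) + in-window days − length of the solicited period + 1. For injection site reactions the length is 8 (D0 to D7). Take a graded reaction on D0–D10 with stop date D10:

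- All days recorded: ongoing, 10 + 8 − 8 + 1 = 11 overall days.
- Only D7 blank, post-window grade and stop date recorded: if kept as ongoing, 10 + 7 − 8 + 1 = 10 overall days.
- The same data under 4.4.2.1.7: not ongoing. The stop date is not used and no overall-days value is derived.

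The in-window count with D7 blank is 7 days whichever status is assigned, because 4.4.2.1.5 uses the daily intensities and not the ongoing status. The lowest overall-days category is 2–3 days. That fits a table for ongoing reactions only: one day on D7 and a stop on D8 gives 8 + 1 − 8 + 1 = 2. The affected reaction is thus lost from that derivation, not shown in it as a shorter one.

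**The case against.** Several counter-arguments have force.

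- **The gaps may be few.** The protocol has sites interview subjects about incomplete entries and explain all missing information (11.1), run consistency checks with queries (11.2) and obtain verbal clarification of missing diary data (13.2). Section 9.2.2.3.2 also has solicited items, including injection site reactions, recorded to D14, a week beyond the injection site window. This stands and limits the size, not the direction.
- **A blank post-window record is often right.** It is expected when a reaction ended within the window. This stands, so only cases without a recorded None and with evidence of persistence need changing.
- **The two-part rule works for graded reactions,** since they have an intensity record too. Correct: what fails for them is the stated reason for ignoring the flag.
- **The last daily intensity might mean the last non-missing one.** The text does not say so, Missing is itself a daily intensity, and the post-window half does not depend on that reading.

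A reader might infer three stronger things that the documents do not support.

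- **That safety endpoints 2 and 3 are understated.** They name number of days of occurrence, time to onset and intensity for reactions up to D7 or D14. The in-window variables do not use the ongoing status.
- **That late-worsening reactions are graded too low.** Section 4.4.2.1.2 says the maximum is "calculated as the maximum of the daily intensities over the period considered". That period is not limited to the solicited window, and the preceding section derives a post-window maximum. The wording is ambiguous, not a demonstrated error.
- **That the booster is favoured over placebo.** The rule is the same in both groups, and no differential effect is shown.

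**Conclusion.** The point holds as a minor defect in a descriptive safety derivation. As written, the rule turns a missing last-day or post-window intensity into not ongoing, no other SAP section corrects this, and the error has one direction: a lower count of ongoing reactions, with the affected reactions lost from overall days. In-window occurrence, days and intensity are unaffected, as is the primary immunogenicity analysis.

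The direction follows from the text alone. The size cannot be established: the 4% to 19% is illustrative and rests entirely on assumed, independent missing rates of 2% to 10% in each field, which data clarification may bring lower.

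**What to change.** In SAP 4.4.2.1.7:

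- Keep not ongoing whenever either recorded value is None.
- When one or both values are Missing and neither is None:
  - for pain, headache, malaise, myalgia and asthenia, set the status from the investigator's ongoing flag or a post-window stop date, and code Missing if neither is available;
  - for erythema, swelling and fever, code Missing if the flag is Yes or a post-window stop date exists. The size and temperature thresholds keep their role wherever values are recorded.

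Carry Missing status into the existing missing category of overall days (4.4.2.1.6), and report the number of affected reactions by group. No change to 4.4.2.1.2 is needed for this point.

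The cost is SAP wording and programming. The SAP already refers to the flag, the stop date and the post-window record, so no new data collection or site work is required.

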4.4.2.2 Unsolicited Non-serious Adverse Events

4.4.2.2.1 Presence

An observation will be considered as an event if it has at least a verbatim term and is not a Grade 0 intensity event. Grade 0 events should be included in the listing "Unsolicited non-serious adverse events not included in the safety analysis".

4.4.2.2.2 Intensity

Intensity for unsolicited non-serious AE will be derived according to the following classification: None, Grade 1, Grade 2, Grade 3, or Missing.

If the unsolicited non-serious AE is measurable and its preferred term is part of the list of solicited reactions, then the measurement is derived based upon and following the same rule than the intensity scales defined in the protocol for that measurable injection site or systemic reaction.

Intensity for the other unsolicited non-serious AEs will correspond to the value reported in the CRF.

The maximum intensity corresponds to the highest intensity for a unique term.

4.4.2.2.3 Last Vaccination

Last vaccination before an unsolicited non-serious AE is derived from the visit numbers provided in the clinical database and is calculated as follows:

- If an unsolicited non-serious AE has a non-missing visit number, the visit number should be used to determine the last vaccination before the unsolicited non-serious AE
- If the visit number is missing, then the start date should be used to determine the last vaccination before the unsolicited non-serious AE

4.4.2.2.4 Time of Onset

Time of onset is derived from the start date of the unsolicited non-serious AE provided in the clinical database and the date of last vaccination:

- start date of the unsolicited non-serious AE - date of previous vaccination

The time of onset should be considered as missing only if one or both of the dates are missing or partially missing.

The unsolicited non-serious AEs will be analyzed “Within 28 days”, which corresponds to AEs with a time to onset between 0 and 28 days after vaccination or missing. An AE with missing time of onset will be considered to have occurred just after the vaccination indicated by the visit number, so will be included in these tables.

Note: Unsolicited non-serious AE that occurred before vaccination (negative time of onset) or with a time of onset higher than defined above will not be included in analysis, but will be listed separately.

Time of onset will be displayed by period as follows: D0-D3, D4-D7, D8-D14, \geq D15 and Missing.

4.4.2.2.5 Duration

Duration is derived from the start and stop dates of the unsolicited non-serious AE provided in the clinical database:

- stop date of unsolicited non-serious AE - start date of unsolicited non-serious AE + 1.

The duration should be considered as missing only if one or both of the start and stop dates of the unsolicited non-serious AE is missing or partially missing.

Duration will be displayed by period as follows: 1-3 days, 4-7 days, 8-14 days, 15 days or more, Missing.

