9.2.2.3.3 Unsolicited Non-serious Adverse Events From Day 0 to Day 28 After Vaccination

In addition to recording solicited reactions, subjects (or subjects' parent(s) / legally acceptable representative(s)) will be instructed to record any other medical events that may occur during the 28-day period after vaccination. Space will be provided in the DC for this purpose.

For each unsolicited non-serious AE, the following information is to be recorded:

- Start and stop dates^a
- Intensity of the event:
 - For measurable unsolicited non-serious AEs that are part of the list of solicited reactions, the size of the AE as well as the temperature for fever will be collected and analyzed based on the corresponding scale used for solicited reactions (see [Table 9.1](#) and [Table 9.2](#))
 - Other unsolicited non-serious AEs will be classified according to the following intensity scale:
 - Grade 1: No interference with activity
 - Grade 2: Some interference with activity
 - Grade 3: Significant; prevents daily activity
- Action taken for each AE, if any (e.g., medication)

The action taken by the subjects (or subjects' parent(s) / legally acceptable representative(s)) to treat any **unsolicited AEs** will be classified in the CRF using the following scale:

- 0: None
- 1: Medication (self-medication with an existing prescription or over-the-counter medication)
- 2: Health care provider contact (no new medication prescribed)

^a The stop date of all related AEs will be actively solicited. For other events, the investigator will provide the stop date when it becomes available. AEs for which no stop date was obtained during the course of the trial will be considered as ongoing at the end of the trial.

3: Health care provider contact and prescription of a new medication (health care provider instructed subject to take a new medication, either an over-the-counter medication or one requiring a written prescription)

- Whether the AE led to discontinuation
- Whether the AE was related to vaccination (for unsolicited systemic AEs). See [Section 9.2.2.3.6](#) for the assessment of causality.

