4.4.2.3.3 Duration

Duration will be computed using the same methodology than for unsolicited non-serious AEs described in [Section 4.4.2.2.5](#).

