5.3.2.5 Start Date and Stop Date

Missing or partially missing start dates for unsolicited AEs will remain missing and not be imputed. If either the start or stop date is missing or partially missing, the time to onset will be considered to be missing. Nevertheless unsolicited AEs with missing time to onset will be included in analyses according to the visit collected.

Missing or partially missing stop dates for AEs (solicited reactions and unsolicited AEs) will remain missing and not be imputed.

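### Adverse events with no stop date go into the 'Missing' duration row, although the protocol treats them as ongoing, and some ongoing solicited reactions are set to missing when their top category is already certain

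*SAP*

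**What the plan says.** Duration is a named attribute of safety endpoints 1, 4 and 6 (Protocol 9.2.2.2; SAP 4.2.2.1). The safety methods in SAP 5.1.2.2.2 say that unsolicited AEs and non-serious AESIs will be described by it.

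**Unsolicited non-serious AEs.** SAP 4.4.2.2.5 computes duration as "stop date of unsolicited non-serious AE - start date of unsolicited non-serious AE + 1". The rule for absent dates is "The duration should be considered as missing only if one or both of the start and stop dates" are missing or partial. The display is fixed: "Duration will be displayed by period as follows: 1-3 days, 4-7 days, 8-14 days, 15 days or more, Missing". SAP 5.3.2.5 adds: "Missing or partially missing stop dates for AEs (solicited reactions and unsolicited AEs) will remain missing and not be imputed".

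**Protocol convention.** Footnote a to Protocol 9.2.2.3.3 reads: "AEs for which no stop date was obtained during the course of the trial will be considered as ongoing", meaning ongoing at the end of the trial. The same footnote says that stop dates are actively sought for related AEs only. For other events the investigator supplies the date when it becomes available.

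**Solicited reactions.** For a reaction ongoing at the end of the solicited period with a missing or incomplete stop date, SAP 4.4.2.1.6 says "the overall number of days of occurrence will be considered as Missing". SAP 4.4.2.1.7 defines ongoing as at least Grade 1 on the last solicited day and at least Grade 1 at some point afterwards.

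**SAEs.** SAP 4.4.2.3.3: "Duration will be computed using the same methodology than for unsolicited non-serious AEs".

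**The concern.** The protocol gives a missing stop date a meaning, and the SAP duration table discards it. No SAP section carries the convention into the duration of unsolicited AEs, and SAP 5.7, which lists changes to the planned analyses, does not mention dropping it.

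The information is hard to recover elsewhere. The items that Protocol 9.2.2.3.3 lists for a non-serious AE are start and stop dates, intensity, action taken, discontinuation and relatedness. Outcome is not among them, so the stop date is the only listed sign of resolution. The 'Missing' row also holds AEs with an unknown start, because SAP 4.4.2.2.4 keeps AEs with a missing time of onset in the 28-day tables. A reader looking for persistent events after the booster cannot separate the two kinds.

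For solicited reactions the recorded grades can already prove that the top category was reached, and the SAP still reports missing.

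**Working it through.** No figure in the plan needs reproducing here. The check sets the rules side by side and applies the SAP's own formulas.

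**1. Where an unsolicited AE with a known start and no stop date goes**
- Protocol 9.2.2.3.3, footnote a: ongoing at the end of the trial.
- SAP 4.4.2.2.5: 'Missing', together with AEs that have a missing or partial start date or a partial stop date.

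**2. Minimum duration if the protocol convention is taken at face value**

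Inputs: onset D0 to D28 (SAP 4.4.2.2.4); Visit 4 at D28 to D35; 1-year visit from D335 (365 - 30); Visit 7 from D700 to D760 (730 ± 30), from SAP Table 3.1, taking 24 months as 730 days. Formula: last contact day - onset day + 1.

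| Last contact | Onset D0 | Onset D28 | Onsets that reach 15 days |
|---|---|---|---|
| D28 | 29 | 1 | up to D14 (28 - 14 + 1 = 15) |
| D35 | 36 | 8 | up to D21 (35 - 21 + 1 = 15) |
| D335 | 336 | 308 | all |
| D700 | 701 | 673 | all |
| D760 | 761 | 733 | all |

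At the final analysis, a completer's AE that really is ongoing has lasted at least 700 - 28 + 1 = 673 days. At the Day 28 analysis the lower bound often does not reach 15 days.

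**3. Solicited reactions**

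SAP 4.4.2.1.6: overall days = (stop day - vaccination day) + n - L + 1. Here n is the number of graded days in the solicited period and L is its length. L is 15 for D0-D14 and 8 for D0-D7, matching the top rows of SAP 4.4.2.1.5. An ongoing reaction has at least one graded day after the period, so the earliest stop is D15 or D8.
- Systemic: 15 + n - 15 + 1 = n + 1. With n = 15 the minimum is 16 days. The '≥ 15 days' row is certain once n is 14 or more.
- Injection site: 8 + n - 8 + 1 = n + 1. With n = 8 the minimum is 9 days. The '≥ 8 days' row is certain once n is 7 or more.

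Without a complete stop date the SAP tabulates all of these as missing.

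**4. Size**

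Count shown in '15 days or more' = true count - k, where k is the number of AEs that lasted 15 days or more but have no complete stop date. The error can only be downward. The documents give no basis for k.

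**The case against.** The strongest reply is that a missing stop date does not prove an unresolved event. Stop dates are actively sought only for related AEs, so on an unrelated AE the date may simply never have been obtained. 'Considered as ongoing' is then a recording convention and not an observation. This stands. A reader might infer that the missingness is caused by non-resolution, or that 673 days is a known minimum. The documents support neither for unrelated AEs, and the 673 days holds only under the convention. For the same reason, moving every such AE into '15 days or more' could create the opposite error.

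Other points that stand:
- 'Missing' is a displayed row, so no event disappears, and long AEs with a recorded stop date are classified correctly.
- Days within the solicited period are tabulated separately (SAP 4.4.2.1.5), so a systemic reaction on all of D0-D14 does appear there as 15 days. The defect is confined to the overall number of days. Its 'missing' row covers only reactions already derived as ongoing.
- A reader might infer that long SAEs are hidden too. SAP 4.4.2.3.3 copies the duration rule, and SAP 4.4.2 counts the SAE form among unsolicited AEs. But endpoint 5 names only occurrence, and the SAE description in SAP 5.1.2.2.2 lists nature, seriousness, outcome and relationship, not duration. No SAE duration table is specified, and outcome is reported.

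The no-imputation policy does not answer the point. A separate row, or a lower bound from grades already recorded, imputes no date.

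**Conclusion.** The point holds for two descriptive outputs. The duration table for unsolicited non-serious AEs does not follow the protocol convention: it mixes AEs that the protocol calls ongoing with AEs of unknown dates, and it can understate '15 days or more'. The overall-days table for solicited reactions sets some reactions to missing when the top category is already certain (at least 16 days systemic, at least 9 days injection site, when every solicited day is graded).

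The direction of any error is known, but its size is not. A reader might want to attach a percentage to the understatement. The documents give neither the share of AEs without a stop date nor the share lasting 15 days or more, so any percentage would only restate the assumed inputs.

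The solicited-reaction result rests only on the SAP's formula and its definition of ongoing. The unsolicited result rests on the protocol convention being the intended reading of a missing stop date. Incidence counts, analysis sets and the primary test are unaffected. It is a modest point, worth correcting because it is cheap and concerns a named endpoint attribute.

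**What to change.** - **SAP 4.4.2.2.5:** add a separate row, 'Ongoing / no stop date', for AEs with a known start date and no stop date. Add a footnote citing the convention in Protocol 9.2.2.3.3. Where useful, give the number in that row whose last contact (or data cut-off) minus start plus 1 is at least 15 days. Keep 'Missing' for missing or partial start dates and for partial stop dates. Do not move AEs into '15 days or more' automatically.
- **SAP 4.4.2.1.6:** assign '≥ 8 days' or '≥ 15 days' when the recorded days plus the ongoing status under 4.4.2.1.7 already reach that limit. Otherwise keep 'missing'.
- **SAP 4.4.2.3.3:** apply the new row to SAEs only if SAE duration is tabulated.

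The cost is SAP wording and a few lines of code, with no new data. The duration tables may look slightly less favourable.
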